1.0 INTRODUCTION

1.1. Canonical use and mechanism of action of metformin

Metformin is an oral anti-hyperglycemic drug widely prescribed for the treatment and maintenance of diabetes mellitus type 2 (1). This biguanide drug is a derivative of a compound first isolated from the *Galega officinalis* (French lilac), which has been used to treat type 2 diabetes since the early eighteenth century (2). Metformin's ability to lower fasting blood glucose concentrations is attributed to its ability to suppress hepatic gluconeogenesis and increase glucose uptake and utilization in muscle and visceral tissues; however, its precise molecular mechanism of action is unclear (3, 4). It is generally accepted that one of metformin's main actions is activation of 5' AMP-activated protein kinase (AMPK), to modulate metabolic and lipid signaling. In hepatocytes, metformin treatment leads to an increase in phosphorylated (active) AMPK, and subsequent phosphorylation of Acetyl-CoA carboxylase at Ser79 (P-ACC-Ser79), a direct biomarker of AMPK activity (5). Whether or not this effect is completely responsible for the underlying cause of metformin's anti-hyperglycemic properties remains controversial (3). Other AMPK-independent activities of metformin that may play a considerable role in its pharmacologic effects include weak and transient inhibition of mitochondrial respiratory chain complex I, and tissue sensitization to insulin action (6, 7).

Unlike other anti-diabetic agents, metformin reduces hyperglycemic blood glucose concentrations without stimulating insulin secretion, hypoglycemia, or promoting weight gain. Additionally, through its role as an AMPK agonist, metformin has been shown to decrease free fatty acid concentrations in plasma, and regulate lipid homeostasis in patients (8, 9). This added benefit is especially important as type 2 diabetics are often at higher risk for cardiovascular disease (10). These numerous effects, combined with its relatively benign toxicity profile and low financial cost are what make metformin the recommended first-line therapy for treatment of type 2 diabetes mellitus, despite the controversy and limited understanding of its molecular mechanism of action.

1.2. Metformin Pharmacokinetics

While metformin is generally well-tolerated by patients, the anti-hyperglycemic response between patients is quite variable. With a twice-daily (BID) oral dose of 750 mg, metformin has a plasma elimination half-life of approximately 6 h. Absorption of the tablet occurs predominately in the small intestine, and is mediated through plasma membrane monoamine transporters (PMATs). However, this absorption is often incomplete, resulting in substantial inter-patient variation in drug bioavailability. Mean drug bioavailability is 55% +/- 16%. Because of this, there is large inter-individual variability in metformin pharmacokinetics (11). Steady-state metformin plasma concentrations can range from 54 to 4133 ng/mL (12). While no accumulation in plasma has been seen in patients after multiple doses, metformin elimination is bi-phasic. While initial elimination of metformin from plasma is relatively rapid, there is a second more prolonged elimination phase possibly due to slow uptake and release from a secondary compartment in tissues (11, 13). Metformin exists as a hydrophilic cationic species at physiologic pH, and as such, has severely limited passive diffusion through tissues. Despite this, metformin is still widely distributed throughout the body and is transported to the liver and other peripheral tissues mainly through organic cation transporters 1 and 3 (OCT1/3) (14). Metformin is not metabolized, is poorly plasma protein-bound and is eliminated from the body by renal excretion into the urine (15).

1.3. Metformin as an anti-cancer agent

Within the last decade, a multitude of studies have suggested that metformin has potential use as an anti-cancer therapeutic. Patients with Type 2 diabetes mellitus have a significantly increased risk of developing colon, prostate, endometrial, breast, ovarian, kidney, and pancreatic cancers (16). Epidemiologic studies revealed that diabetic patients receiving metformin had both lower incidence and later onset of cancers compared to diabetics who were not taking metformin (17-23). Diabetics on metformin also had lower incidence of cancers compared to non-diabetics (24). Preclinical studies have shown that metformin elicits anti-proliferative effects in a variety of cancer cell lines both *in vitro* and *in vivo* (3, 19, 25). However, as with its mechanism of anti-diabetic activity, the mechanism of metformin's anti-cancer activity is unclear and controversial.

The AMPK-dependent inhibition of mTORC1 in cancer cells is one of the potential key mechanisms that facilitates the anti-cancer activity of metformin. AMPK activation leads to mTORC1 inhibition at multiple concentrations via direct phosphorylation of raptor protein, and indirectly through activation of tuberous sclerosis 2 protein (TSC2) (26-28). Metformin treatment of MCF-7 breast cancer cells results in cell growth inhibition via an AMPK-dependent decrease in phospho-S6 (26). As mTORC1 inhibiting agents are already used clinically to treat a number of cancers, metformin may be an already-FDA-approved, less toxic, and relatively cheap mTORC1-inhibiting agent. In fact, in comparing *in vivo* metformin treatment to the mTORC1 inhibitor rapamycin, metformin also decreases activation of AKT upstream of mTORC1 (28). As AKT signaling has been associated with resistance to mTORC1 inhibition, metformin may be rendering a more efficient anti-cancer response than conventional mTORC1 inhibitors.

While the above is a widely accepted mechanism of metformin's anti-cancer activity established *in vitro*, there is another school of thought suggesting that metformin's preventative anti-cancer effects (seen epidemiologically) stem from its ability to systemically regulate insulin signaling independent of metformin's direct action on AMPK. Increased cancer risk associated with Type 2 diabetes mellitus is thought to be a result of constitutively elevated plasma insulin concentrations. Insulin promotes carcinogenesis through insulin receptor signaling, as well as indirectly through increasing concentrations of insulin-like growth factors, sex hormones, and inflammatory processes (29, 30). Metformin can lower circulating insulin concentrations, thus reducing the potential mitogenic effects of insulin on tumor cells (6).

1.4. Translatability of *in vitro* findings to *in vivo*

Despite the disagreement surrounding its molecular mechanism of action, a multitude of clinical trials attempting to provide proof of concept for the direct anti-tumor activity of metformin have been launched and met with conflicting results (25, 31). In investigating why there is so much variability between trials, one problem is that a majority of these trials failed to assess what concentrations of metformin were actually reaching cancerous tissues. As discussed previously, both the pharmacokinetic and therapeutic properties of metformin can vary greatly between patients. Also, a majority of the preclinical evidence claiming metformin as an effective anti-cancer agent were done with supra-pharmacologic concentrations of metformin (5-50 mM), such concentrations are not achievable in humans. We and others have performed preclinical pharmacokinetic studies in animals to obtain a better understanding of achievable tissue concentrations of metformin in animal models of cancer. Dowling *et al.* recently showed that standard mouse models in which metformin elicits anti-cancer activity (at a dose of 0.5 mg/kg/d in drinking water) are likely an approximation of high-dose metformin administration in humans, achieving much higher than typical plasma concentrations than we see with normal human dosing (plasma concentrations ranging from 297 to 16,274 ng/mL, which equal 0.45- 24.3 μ M) (32). We have found that a lower dosing regimen (0.1 mg/kg/d in drinking water) in mice can

still produce a robust anti-cancer effect in MCF-7 xenografts and is sufficient dosing to activate AMPK signaling in tumor tissues. Using this treatment regimen, mouse plasma steady-state concentrations ranged from 389 to 829 ng/mL (0.58-1.24 uM), more reflective of human steady-state plasma concentrations (54 to 4133 ng/mL, which equal 0.08- 6.21 uM). Additionally, tumor tissues reached metformin concentrations in the 100-nM range (unpublished data). In parallel, our studies in cultured MCF-7 cells revealed that treatment with ~1 mM metformin—the lowest dose of metformin required to elicit AMPK activation in culture—achieves intracellular concentrations of approximately 10 uM (unpublished data). As this concentration is substantially above what we see accumulate in tumor tissue, and yet, we still see AMPK activation in said tumor tissue with only nM concentrations, there must be vastly different dynamics of drug response to metformin between *in vivo* and tissue culture (32).

To better understand metformin's anti-cancer effects in humans, it is first crucial to assess what concentration of metformin is achievable in both normal and cancerous tissues, and the degree of inter-patient variability. If the insulin-independent effects of metformin are predominately responsible for its' anti-cancer activity (as preclinical studies widely claim), then assessing the concentrations of metformin in tumor tissues, and whether those concentrations are sufficient to activate AMPK and inhibit mTORC1, are the first steps to beginning to better understand the variability in clinical trial data.

1.5. Study rationale

We propose to conduct a presurgical (proof of principle, window of opportunity) study in patients with surgically resectable thoracic tumors to determine steady-state tissue and plasma concentrations of metformin. To understand the variability in clinical results testing metformin as an anti-cancer agent, it is important to determine the concentrations of metformin that are achievable in tissue. Clinical effects of metformin develop gradually over several days of treatment. Steady-state plasma metformin concentrations are correlated with anti-hyperglycemic response. Thus, achieving steady-state concentrations in this study will allow accurate determination of the most representative concentrations of metformin in normal and cancerous tissues, as well as determine AMPK signaling differences in these tissues. As our Primary Objective is to determine the concentration of metformin in tumors, we will treat patients with metformin extended release (ER) (Glucophage® XR), starting at 750 mg PO QD for 4 days, then escalating to 750 mg PO BID for 3-6 days prior to surgery. FDA prescribing information indicates that metformin reaches steady-state plasma concentrations within 24-48 hours after the start of dosing in humans; thus, the 7-to-10-day time frame of our study will allow sufficient time for metformin to reach steady-state plasma concentrations, in addition to time allotted for potential accumulation in tissues. Metformin concentrations will be measured using a validated LC-MS/MS assay.

2.0 OBJECTIVES

2.1 Primary Objective

To determine the intra-tumor concentrations of metformin, with a standard deviation $\leq 25\%$ of the mean, in patients with solid tumors of thoracic origin administered metformin extended release.

2.2 Secondary Objective

To determine the concentration of metformin in adipose tissue, tumor-adjacent normal tissue, plasma, and whole blood.

2.3 Exploratory Objective

To determine whether metformin alters AMPK activity in tumor cells.

3.0 ELIGIBILITY CRITERIA AND PARTICIPANT REGISTRATION

Inclusion Criteria:

- 3.1 Patients with confirmed or suspected malignant solid tumor of thoracic origin (e.g., lung, esophageal, thymus, mesothelioma, chest wall, mediastinum, trachea, pleura) with the intent to treat or biopsy by surgery as standard of care. Tumor must be ≥ 1.5 cm.
- 3.2 Patients with multicentric disease are eligible. Samples from all available tumors are requested for research purposes.
- 3.3 Patients with T2DM being treated with metformin (any dose) for a clinical indication at the time of study enrollment are eligible, and will continue metformin treatment as clinically indicated during the presurgical study period. Their dose of metformin will NOT be changed.

Patients not on metformin at the time of study entry must be willing to take metformin extended release (Glucophage® XR, 750 mg QD for 4 days, then 750 mg BID for 3-6 days) for a total of 7-10 days prior to surgery.

Patients do not require a diagnosis of diabetes to be enrolled in the study.

All patients must be willing to keep a drug diary indicating the dates and times of metformin administration.

One patient who has not been treated with metformin will be consented and enrolled. This patient will be asked to provide tumor, adipose, normal lung tissue, and blood samples, and all samples will be collected as described in section 4.2.2. These samples will be taken to serve as a control and are needed in order to optimize the metformin quantification.

- 3.4 Patients must meet the following clinical laboratory criteria:

- Absolute neutrophil count (ANC) $\geq 1,500/\text{mm}^3$ and platelet count $\geq 75,000/\text{mm}^3$.
- Total bilirubin $\leq 1.5 \times$ the upper limit of the normal range (ULN).
- Alanine aminotransferase (ALT) and aspartate aminotransferase (AST) $\leq 3 \times$ ULN.
- eGFR $> 60 \text{ mL/min}/1.73\text{m}^2$ or eCrCL $> 60 \text{ mL/min}$
- [name] Question For lung surgery do we need an INR < 1.6

- 3.5 Ability to give informed consent.

- 3.6 Patients must be willing to provide 20 mL of blood for research use.

- 3.7 Patient must be willing to provide consent for use of archived tissue for research.

Exclusion Criteria:

- 3.8 History of diabetes that is currently being treated without metformin.
- 3.9 Patients with a documented history of alcoholism, or binge drinking disorder.

3.10 Patients who, at the time of study entry, are not taking metformin for a clinical indication, and who will need a radiographic analysis with an iodinated contrast agent during the metformin study treatment period.

This criterion does not apply to patients taking clinically indicated metformin at the time of study entry.

3.11 History of reactive hypoglycemia.

3.12 History of liver disease as defined with LFTs above those in the inclusion

3.13 Known hypersensitivity to metformin.

3.14 Active or history of lactic acidosis, metabolic acidosis, or diabetic ketoacidosis.

3.15 Patients who are pregnant or breastfeeding.

Participant Registration:

3.16 Following completion of pre-treatment evaluations and informed consent, participants will be registered by a Clinical Research Coordinator via the Norris Cotton Cancer Center's clinical trials management system (Velos or equivalent) . At the time of registration, the following information will be recorded:

[figure not shown]
- Patient's name and subject identification number.
- Patient's date of birth.
- Date of treatment start.

3.13 Eligibility criteria will be verified at the time of registration. A case number will be assigned following registration.

4.0 TREATMENT PLAN

4.1 Screening Period

Subjects will provide written informed consent, be evaluated for eligibility criteria, and undergo standard baseline clinical and tumor assessments and staging. Subjects will undergo our standard pre-treatment surgical evaluation.

4.2 Treatment Period

Patients who are not taking metformin at the time of study enrollment will receive oral metformin extended release (Glucophage® XR, 750 mg tablets). Metformin is to be taken with a meal as one 750-mg pill per day for the first 4 days, followed by two 750-mg pills per day (one pill in morning, one pill in evening), for a total pre-surgical metformin regimen of 7-10 days (as depicted in schematic above). The last dose of metformin extended release should be taken at 7:00 pm (+/- 1 hour) the night preceding the surgery.

Patients already taking metformin for a clinical indication at the time of study enrollment will continue their metformin regimen while on study. The last dose of metformin should be taken the night preceding the surgery. A record will be kept regarding which patients are not taking the 750 mg BID dosing of metformin and this will be noted in the analysis.

All patients will record the dates and times of metformin ingestion on the evening before surgery in a drug diary.

A single patient who has not been treated with metformin will be consented and enrolled. This patient will be asked to provide tumor, adipose, normal lung tissue, and blood samples, and all samples will be collected as described in section 4.2.2. These samples will be taken to serve as a control and are needed in order to optimize the metformin quantification.

4.2.1. *Presurgical metformin*

Patients enrolled will be treated with metformin (administered orally; 750 mg QD for 4 days, then 750 mg BID for 3-6 days; or clinically indicated metformin) for a total of 7-10 days prior to surgery, up until the night before surgery.

4.2.2. *Surgery and biological specimens*

Specimens will be acquired and processed as described in Appendix A.

Plasma and Whole Blood

On the morning of surgery, 20 mL of blood will be collected for research purposes in the pre-operative area. This blood may be collected at the same time as a routine clinically indicated blood draw or during placement of an intravenous line (before saline is administered), and should occur as close to the time of surgery as possible. Blood will be drawn into (2) 10-mL purple-top (EDTA-treated) tubes, picked up by a member of the [name] Lab within 1 hour of being drawn from the patient, and processed by the [name] Lab as in Appendix A.

In the [name] Lab, a 10-mL blood sample will be centrifuged at 1,000 x g for 30 minutes at 4°C to separate plasma, which will be aliquoted into cryovials (1 mL/vial). The other 10-mL blood sample will be aliquoted into cryovials (1 mL/vial) as whole blood. All plasma and whole blood sample aliquots will be stored at -80°C until analysis.

Tumor tissue, adipose tissue, and normal adjacent tissue

Requested specimens: Tumor tissue fragment ≥ 8 mm in diameter*

Adipose tissue fragment ≥ 8 mm in diameter*

Normal adjacent tissue fragment ≥ 8 mm in diameter*

* small tissue fragments may be pooled to yield ≥ 8 mm of tissue

The patient will undergo surgical resection or biopsy of the tumor(s). During the procedure, the surgeon will attempt to obtain a sample (≥ 8 mm in diameter) of adipose tissue (likely subcutaneous) and normal adjacent tissue (such as lung, when available) (≥ 8 mm in diameter) when feasible.

All normal and tumor tissues will be sent to Pathology for dissection. The Pathologist or her/his designate will promptly dissect the surgical specimen(s). ASCO-CAP guidelines require initiation of dissection of a surgical specimen within 1 h of removal from the patient; for this study, minimal lag time (“cold ischemia time”) is preferred.

The Pathologist will assess whether the tumor specimen is large enough to procure:

- A. tissue for routine diagnostics.
- B. ≥ 6 tumor fragments that are ≥ 4 mm³ in all dimensions for research use.

A 1.5-cm tumor is expected to provide sufficient material for all needs.

If the tumor is too small to provide adequate tissue for research, the tumor will be considered non-evaluable and the patient will need to be replaced.

Tissue specimens procured for research purposes will be cut into 4-mm³ fragments, weighed, and individually frozen in cryovials by a member of the [name] lab. Tissue specimens with overt blood content will be pressed between absorbent towels to remove blood prior to weighing. Please see SOP in Appendix A for tissue handling/processing and storage.

All research tissue samples should be frozen within 1.5 h of tissue removal from the patient; a shorter lag time is strongly preferred to preserve phospho-proteins.

4.2.3. *Metformin drug information*

Metformin (1, 1-Dimethylbiguanide hydrochloride) is a synthetic biguanide derivative. Administered orally, this drug is predominately used to help lower blood glucose concentrations in diabetes mellitus type 2 patients. Metformin effectively lowers blood glucose concentrations in patients by decreasing hepatic glucose output, and increase peripheral glucose uptake and utilization (3, 4). Metformin also decreases circulating insulin and fatty acid concentrations in patients (8).

Preclinical and pharmacodynamic data in humans

Oral metformin is absorbed in the small intestinal tract and taken up through plasma membrane monoamine transporters (PMATs). Metformin is predominantly transported into cells via organic cation transporters (OCT1/3). Metformin has a plasma half-life of 5-6 h (11). Due to inter-patient variability in drug absorption and transport, steady-state metformin plasma concentrations can range from 0.054 to 4.133 ug/mL (0.08- 6.21 uM) (15). Estimated therapeutic concentrations of metformin range from 0.129 to 90 ug/mL (0.19 uM to 132.9 uM) (33).

Selectivity of metformin

Metformin is canonically an agonist of AMPK; however it has also been reported to weakly inhibit mitochondrial respiratory complex 1 *in vitro* (5, 7). In diabetics, metformin systemically lowers blood glucose concentrations by inhibiting hepatic

glucose output and increasing glucose utilization, without causing hyperinsulinemia, hypoglycemia, or promoting weight gain (3). Metformin also systemically increases insulin sensitivity and decreases concentrations of circulating fatty acids (6).

Toxicities and risks of metformin

In worldwide placebo-controlled clinical trials, 781 patients with type 2 diabetes were administered metformin extended release (Glucophage® XR; 500 or 750 mg), and 195 patients received placebo. Adverse reactions reported in >5% of the metformin extended release-treated patients, and that were more common in metformin extended release-treated than placebo-treated patients, are noted in the table below [extracted from Glucophage® product insert (34)].

Adverse Reaction	GLUCOPHAGE XR (n=781)	Placebo (n=195)
	% of Patients	
Diarrhea	9.6	2.6
Nausea/Vomiting	6.5	1.5

Diarrhea led to discontinuation of study medication in 0.6% of patients treated with GLUCOPHAGE XR (metformin extended release). Additionally, the following adverse reactions were reported in ≥1.0% to ≤5.0% of GLUCOPHAGE XR patients and were more commonly reported with GLUCOPHAGE XR than placebo: abdominal pain, constipation, distention abdomen, dyspepsia/heartburn, flatulence, dizziness, headache, upper respiratory infection, taste disturbance. Cholestatic, hepatocellular, and mixed hepatocellular liver injury have been reported with post-marketing use of metformin. In rare cases, metformin treatment can result in lactic acidosis; the main risk factors for this serious adverse event are renal impairment, or overdose of drug. While this lactic acidosis toxicity is uncommon, it is recommended that patients not be prescribed metformin if their plasma creatine values are above 1.5 mg/dL (men) or 1.4 mg/dL (women) (35).

Metformin extended release will be stored, dispensed, and accounted for by the DHMC Investigational Pharmacy.

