8.0 STATISTICAL CONSIDERATIONS

8.1 PRIMARY ENDPOINT – Concentrations of metformin in tumor tissue.

8.2 SECONDARY ENDPOINT – Concentrations of metformin in adipose tissue, tumor-adjacent normal tissue, plasma, and whole blood.

8.3 EXPLORATORY ENDPOINT – Changes in AMPK activity induced by metformin, as determined by changes in P-ACC and P-S6 histoscores between pre- and post-metformin tissue specimens.

8.4 PRIMARY ANALYSIS PLAN – The primary analysis will measure the concentrations of metformin in biological triplicate samples of plasma, whole blood, and tissue specimens from each patient. Metformin concentrations will then be statistically analyzed to determine A) variability between biological triplicates, B) inter-individual variability between patients (within each tissue type; calculate descriptive statistics), and C) relationships between tissue types within each patient (compared by paired *t*-test or two-way ANOVA).

8.5 EXPLORATORY ANALYSIS PLAN – An exploratory analysis will determine whether metformin treatment significantly alters AMPK signaling in tumors compared to baseline. Histoscores from paired (pre- and post-metformin) tissue specimens will be compared by Wilcoxon rank sum test, and the correlation with metformin concentration will be established (the log transformation may be used to comply with the normal distribution assumption). Furthermore, an exploration of the metformin concentrations in plasma blood and tumor tissue and changes in tumor Histoscores will be undertaken using the direct PK-PD model (e.g., sigmoid Emax).

8.6 STATISTICAL TESTING - All statistical tests will be two-sided, and the overall type I error will be 0.05.

8.7 SAMPLE SIZE – We propose to evaluate 20 patients for the Primary Endpoint to account for the wide range (>75-fold) of steady-state plasma concentrations of metformin previously shown in

humans (12). There are no data on intra-tumor concentrations of metformin. As a surrogate, we will use plasma concentrations of metformin under the assumption that plasma and tumors will exhibit similar ranges of variability between patients. We will enroll one additional subject to acquire control tissues, bringing the total study accrual goal to 21 subjects.

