Requested specimens: Tumor tissue fragment ≥8 mm in diameter*

Adipose tissue fragment ≥8 mm in diameter*

Normal adjacent tissue fragment ≥8 mm in diameter*

* small tissue fragments may be pooled to yield ≥ 8 mm of tissue

All normal and tumor tissue specimens will be sent to Pathology for dissection.

The Pathology Department individual who receives the surgical specimens will immediately notify the [name] Lab that specimens have arrived, and a [name] Lab member will come to Pathology to acquire tissue.

The [name] Lab member will pre-weigh cryovials, and write the vial weight on tube.

To Pathology, the [name] Lab member will bring cryovials, which need to be labeled with the patient study ID (D17188_####), tissue type, date, time of surgery, and time of freezing.

The Pathologist ([name]) or her delegate will assess whether the tumor specimen is large enough to procure:

- A. tumor tissue for routine diagnostics.
- B. ≥ 6 tumor fragments that are ≥ 4 mm in all dimensions for research use.

A 1.5-cm tumor is expected to provide sufficient material for both needs.

All research samples should be acquired within 1.5 h of tissue removal from the patient; a shorter lag time is strongly preferred to preserve phospho-proteins.

In Pathology, research tissue specimens with overt blood content will be gently pressed between absorbent towels to **remove blood**. Tissues will be cut into fragments ≥ 4 mm in all dimensions, and individually placed into cryovials (1 fragment per vial) on ice.

The [name] Lab member will then promptly re-weigh the vials, write the new weight on the vial, freeze vials in liquid nitrogen, and store vials at -80°C.

Time from patient to freezing should be minimized.

- 4) The following data will be recorded in the specimen log book (template in Appendix B) in the [name] Lab:
 - Research ID#
 - Date and time of blood draw and surgery
 - Time that blood, plasma, and tissue fragments are frozen, and numbers of aliquots/specimens
 - Tissue locations and tumor subtypes

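### Blood is drawn before surgery and tissue is removed later with no maximum gap, so a tissue-to-plasma comparison under 8.4(C) would be biased low by an amount the plan neither bounds nor examines

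*Combined protocol and SAP*

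**What the plan says.** **Blood.** Section 4.2.2 states: "On the morning of surgery, 20 mL of blood will be collected for research purposes in the pre-operative area". It adds: "This blood may be collected at the same time as a routine clinically indicated blood draw". Placement of an intravenous line is another permitted occasion, and the draw "should occur as close to the time of surgery as possible". Appendix A repeats this. Neither place sets a limit in hours.

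**Tissue.** Section 4.2.2 places tissue collection inside the operation; for adipose and normal adjacent tissue it says "During the procedure, the surgeon will attempt to obtain a sample". The one time limit is "All research tissue samples should be frozen within 1.5 h of tissue removal from the patient". That clock starts at removal, so it does not bound the interval from blood draw to removal.

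**Dose and decline.** Under 4.2, study-treated patients take their last dose at about 7 pm the evening before surgery. Section 1.2 gives a "plasma elimination half-life of approximately 6 h" and section 4.2.3 gives 5-6 h. Section 1.2 also describes a second, slower elimination phase, without a half-life for it.

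**Analysis.** Section 8.4 lists plasma, whole blood and tissue as the specimens measured. Item C then examines "relationships between tissue types within each patient" by paired t-test or two-way ANOVA. It has no time matching, lag covariate or correction.

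**Records.** Appendix A logs "Date and time of blood draw and surgery". The Appendix B template has a sampling-time column with a row for each specimen type, but does not say which moment counts as sampling for a tissue.

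**The concern.** Within each patient, blood always comes first and tissue second. With no dose on the morning of surgery for study-treated patients, plasma is expected to be lower at tissue removal than at the draw. A ratio of tissue at removal to plasma at the draw therefore understates the ratio at a common moment. Pairing does not remove this, because the shift has the same sign in every patient, and its size varies with each patient's wait.

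At stake is what the trial can say about tumor relative to circulating drug. A paired test could report tumor below plasma when the two are equal at the same moment, or hide a real excess in tumor. The sampling times that would let a reader judge this are collected, but no planned analysis uses them.

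**Working it through.** **The plan's own figure.** The only power figure (section 8.7) is a detectable CV of 15% against a null of 25%, n=20, one-sided alpha 5%, 90% power. With SD on the log scale taken as the CV, power = P[χ²₁₉ < 10.117 × (0.25/0.15)²] = 91.9%, so the figure reproduces. It concerns the tumor CV alone and does not involve plasma. There is no power figure for 8.4(C).

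**Inputs from the protocol.** Half-life h = 5 or 6 h (4.2.3); n = 20 (8.7); two-sided 5% tests (8.6).

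**Inputs assumed, because the documents give none.** Gap L from draw to removal: 0.5, 1 or 2 h. SD of the within-patient log tissue-to-plasma ratio: 0.35 to 1.0. Half-life of the slower phase: 12 h, as an illustration.

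**Step 1: bias in the ratio.** Bias = 1 − 2^(−L/h).

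| Gap | h = 6 h | h = 5 h | h = 12 h (assumed) |
|---|---|---|---|
| 0.5 h | 5.6% | 6.7% | 2.8% |
| 1 h | 10.9% | 12.9% | 5.6% |
| 2 h | 20.6% | 24.2% | 10.9% |

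**Step 2: false rejection when concentrations are truly equal at the same time.** The mean log difference is ln(2) × L/h. The paired t-test has 19 df and noncentrality ln(2) × (L/h) × √20 / SD. Example: L = 1 h, h = 6 h, SD = 0.35 gives a shift of 0.1155, noncentrality 1.48 and rejection 28.9%.

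| Gap | SD 0.35 (h = 6 to 5) | SD 1.0 (h = 6 to 5) |
|---|---|---|
| 0.5 h | 10.8-13.4% | 5.7-6.0% |
| 1 h | 28.9-39.1% | 7.8-9.1% |
| 2 h | 80.0-91.9% | 16.6-21.8% |

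With a 12 h half-life and SD 0.35 the rates are 6.4%, 10.8% and 28.9%.

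**Step 3: would correcting with the 5-6 h half-life be enough?** Suppose the true half-life is 12 h, L = 2 h and SD = 0.35. Uncorrected, the test rejects 28.9%. Correcting with 6 h leaves an error of ln(2) × 2 × (1/6 − 1/12) = 0.1155, the same size with the opposite sign, so again 28.9%. Correcting with 5 h leaves ln(2) × 2 × (1/5 − 1/12) = 0.1617 and rejects 50.1%.

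**Step 4: would regressing the log ratio on the gap be enough?** Its intercept estimates the ratio at zero gap without an assumed half-life, and simulation keeps the error rate near 5%. With gaps spread uniformly over 1-4 h (assumed; mean 2.5, variance 0.75) and SD 0.35, the standard error rises from 0.35/√20 = 0.078 to 0.35 × √(1/20 + 2.5²/(19 × 0.75)) = 0.245, about three times larger.

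**The case against.** - **The target test is inferred.** Item C speaks of tissue types, and section 4.5 lists blood and plasma apart from tissue, with tumor, normal and adipose in brackets. Comparisons among tissues from one operation are a possible reading. This stands as a reason to confirm the intent. But section 8.4 lists plasma and whole blood with the tissues, and section 2.2 makes both secondary measures, so including them is natural.
- **The protocol already shortens the gap and logs times.** This stands in part. At 0.5 h the false-rejection rate is only about 6-13%. But the instruction refers to the time of surgery, not of removal, sets no maximum, and permits a routine draw.
- **Exact equality is an unlikely null.** Section 1.2 describes severely limited passive diffusion, and section 1.4 reports mouse tumor concentrations well below plasma. Against a several-fold true difference, a drift of 6-24% moves the estimate but would rarely change the test's conclusion. This stands, and makes the ratio bias the better measure of size.
- **Decline may be slower than 5-6 h.** Section 1.2's second phase, or continued extended-release absorption, would shrink the bias. This also stands. It is equally why a reader should not infer that a single back-correction at 5-6 h settles the matter: step 3 shows that it can reject as often as no correction, or more often.

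**Conclusion.** The point holds as a minor one. If 8.4(C) compares tissue with plasma or whole blood, the tissue-to-plasma ratio is biased low by about 6-7%, 11-13% and 21-24% for gaps of 0.5, 1 and 2 h at the stated 5-6 h half-life, and by less if decline is slower. A two-sided 5% paired test of truly equal concentrations would falsely reject about 6-13%, 8-39% and 17-92% of the time at those gaps. The gaps and the log-SD range of 0.35 to 1.0 are assumptions, and n=20 is the planned number; fewer pairs are possible for adipose and normal tissue, which are taken only when feasible. The documents give no half-life for whole blood, so the size there is less certain still.

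A reader might infer that the planned comparison is close to certain to give a false result. The documents do not support that: it needs a long gap, a small log-SD, 5-6 h decline and exact equality all at once. Nor is the primary endpoint compromised. Tumor concentration and its CV calculation do not use plasma. The plasma and tumor exploration in 8.5 does share the time mismatch.

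**What to change.** 1. **Section 8.4(C).** State whether plasma and whole blood are included. If so, analyse the within-patient log tissue-to-plasma and log tissue-to-whole-blood ratios, report each patient's gap from blood draw to tissue removal, and keep the uncorrected comparison.
2. **Sensitivity analysis.** Move plasma to the removal time under a range of declines: none, a slow phase (such as an assumed 12 h), 6 h and 5 h. Add a regression of the log ratio on the gap. Claim that tumor is above or below plasma only if the conclusion holds across the range.
3. **Appendix B.** Define the tissue entry for sampling date and time as the moment of removal from the patient.

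The cost is plan wording, one definition in the log and a little more analysis. The downside is precision: under the assumptions in step 4 the gap-adjusted estimate has about three times the standard error, so it belongs beside the uncorrected result and should not replace it.
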